### **Specific Analyses**

Hypothesis 1: GLMM will model each primary relapse risk outcome (craving (QSU), stress reactivity (heart rate and salivary cortisol), and latency to self-administration) as a function of the main effects and interaction between time (pre vs. post) and treatment group, including any necessary control variables (as defined above in the confounding variables section) and a random intercept for participant. Secondary measures of craving and stress reactivity will be assessed in similar fashion with Type I error correction for the frequentist analyses.

Hypothesis 2: GLMM will model each sleep metric (quality, duration, and restlessness) as a function of the main effects and interaction between time (pre vs. post) and treatment group, including control variables and a random intercept for participant. Secondary measures for sleep will be assessed in similar fashion with Type I error correction for the frequentist analyses.

Exploratory Hypothesis GLMM will model each relapse risk outcome (craving, stress reactivity, and latency to self-administration) as a function of the main effects and all higher-order interactions between time (pre vs. post), given sleep metrics (in unique models: quality, duration, and restlessness), and treatment group, including control variables and a random intercept for participant.

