**Research Team PI: [name].** [name] is an Assistant Professor in the Department of Psychiatry & Behavioral Sciences, with a primary research program involving novel applications of biostatistics and data science to health outcomes. However, his recent endeavors have expanded to first-hand research in substance use disorders and psychopharmacology, resulting in two pertinent first-author publications investigating (1) the effects of suvorexant on relapse-related factors in cocaine use disorder and (2) the strongest predictors of the first smoking lapse during a quit attempt. The present study will be supported by the infrastructure and research team at the CNRA, including **[name].**, a frequent collaborator of the PI that will assist in the implementation of the current experimental design, and mentorship from **[name].**, with expertise in psychopharmacology and the neurological bases for addiction.

**Study Medication & Medication Compliance** Participants will be randomized to receive either suvorexant 0 or 20 mg for 7 days. 20 mg is currently the highest FDA-approved dose. The bioavailability of suvorexant is > 80% and it is highly protein-bound, with a half-life of approximately 12 hours and plasma steady-state is reached within three days. Because suvorexant is a hypnotic with a moderate half-life, participants will be informed to take the medication at 10:00 PM. Compliance will be assessed using both Medication Event Monitoring Systems (MEMS) pill bottles that record the time/frequency of bottle openings as well as riboflavin.

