**Stress Reactivity** Stress reactivity will be assessed using a modified version of the CPT on study days 1 and 8. The CPT involves participants submerging their dominant arm in an ice-water bath for up to 2 min. The CPT is widely used to induce stress in human laboratory studies and activates major stress systems in the body. Stress activation can be significantly increased by incorporating a social evaluative component, which will be done by having a study member present wearing a white lab coat and holding a clipboard. Participants will also be videotaped and informed that their facial expressions will be assessed. Stress levels will be assessed using both subjective and physiological measures, including HR, BP, and salivary cortisol, consistent with previous studies from our group.

**Smoking Relapse Assessment** A dual-component smoking relapse assessment will be conducted in which participants will have the opportunity to self-administer their preferred brand of cigarettes. Participants will earn \$1 for every 5 min they do not smoke for the first 50 minutes (for a total of \$10). At 50 minutes or once participants indicate they want to smoke, they will be given \$7 to either purchase their preferred brand of cigarettes (\$1 per cigarette) or keep. The two dependent variables will be latency to smoke the first cigarette and total number of cigarettes smoked.

**Study Compensation** Participants will be provided \$40 for completing the baseline screening. They will receive \$50 for attending each study visit and a \$50 bonus for completing the study/returning study equipment. Additionally, participants will receive \$5 compensation per visit for parking and/or bus fare. As noted above, participants may earn up to \$34 across visits during the smoking relapse assessment (if achieving maximum latency and zero cigarette purchase), bringing total possible compensation to \$234/participant. Upon study completion, participants may be given the opportunity to earn an additional \$20 for referring new participants to the study that successfully enroll and also complete all study procedures.

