**Statistical Modeling** Analyses will primarily use generalized linear modeling (GLM) with multilevel components (GLMM) for correlated observations. Specifically, for each hypothesis, GLMM will model each outcome measure of interest as a function of group, potential confounding variables (as described above), and random effects to account for correlated observations where necessary. Continuous, count, and dichotomous outcomes will utilize normal, Poisson/negative binomial, and binomial distribution families respectively, with identity, log, and logit link functions as appropriate. Evaluation of distributional assumptions will use residual plots, formal statistical tests, and posterior predictive checking. Violations of assumptions will be addressed via transformation, robust estimation, stratification, and/or coefficient scaling where appropriate.

**Missingness & Multiple Comparisons** While the short nature of the proposed trial should reduce the prospect of missing data, for the frequentist analyses, missing data will be addressed via maximum likelihood, explicit modeling of missingness, and/or imputation. Bayesian analyses will use joint modeling of outcomes and missingness to handle missing data. Each approach is robust to ignorable missingness (i.e. MCAR and MAR). Analyses will address non-ignorable missingness using pattern-mixture modeling. Sensitivity analyses will permit evaluation of the robustness of findings to missing data assumptions. While Bayesian analyses are not influenced by traditional concerns of multiplicity, frequentist analyses will utilize false discovery rate (FDR) to control for Type I error across multiple tests for secondary outcomes where delineated.

**Exploratory Data Analyses** Where not otherwise specified, to maximize the utility of the present data, exploratory analyses will evaluate relationships between variables captured as part of the study. For example, while not represented in specific hypotheses, changes in self-reported smoking behavior as functions of other variables in the present study will be explored.

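### Latency to smoking is tested as a time-by-group interaction, although adjusting Day 8 for the pre-dose Day 1 value estimates the same difference, usually more precisely

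*Combined protocol and SAP*

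**What the plan says.** - **Outcome.** The Smoking Relapse Assessment paragraph under Measures pays participants for each 5 minutes of delay up to 50 minutes. The purchase phase opens "At 50 minutes or once participants indicate they want to smoke". It then says "The two dependent variables will be latency to smoke the first cigarette and total number of cigarettes smoked". The Study Compensation paragraph gives the top payment "if achieving maximum latency and zero cigarette purchase".
- **Model.** Specific Analyses, Hypothesis 1: "GLMM will model each primary relapse risk outcome (craving (QSU), stress reactivity (heart rate and salivary cortisol), and latency to self-administration", each "as a function of the main effects and interaction between time (pre vs. post) and treatment group", with a random intercept for participant.
- **Family.** Statistical Modeling: "Continuous, count, and dichotomous outcomes will utilize normal, Poisson/negative binomial, and binomial distribution families respectively". Latency is therefore normal with identity link by default.
- **Covariates.** The Confounding Variables paragraph brings in the stratification variables, plus baseline variables related to both group and outcome. It does not name the Day 1 value of the outcome, which Hypothesis 1 already uses as the pre-treatment response.
- **Timing.** Human laboratory measures are taken on Days 1 and 8. Section E1 calls the first of these the baseline observations. Medication starts on Day 1 (Table 1), and "participants will be informed to take the medication at 10:00 PM".
- **Stratification.** Study Design names FTND severity only. Section E1 names sex, FTND severity and craving.

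**The concern.** Latency is one of the primary relapse risk outcomes and the trial's behavioural measure of relapse. The sample is fixed at 20 by time and budget, so making better use of data already collected is one of the few ways left to gain precision.

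The interaction contrast subtracts the whole Day 1 value from Day 8, whatever the correlation between the two days. Unless that correlation is very high, this adds noise. Regression on Day 1 removes only the part of Day 1 that predicts Day 8. Under randomization, with Day 1 measured before dosing, both contrasts target the same difference. What is at stake is the width of the interval for an effect that the pilot is meant to pass on to a larger trial.

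**Working it through.** **1. The plan's own figure.** Inputs from Sample Size and Power Considerations: N = 20, alpha 0.05, Cohen's f = 0.66, 80% power. Two-group F test with 1 and 18 df and noncentrality f²N = 0.66² × 20 = 8.71: power is 79.7%, and f for exactly 80% is 0.662. The figure reproduces. It equals a two-sided t test on change scores with d = 2f = 1.32 SDs of change, so it fits the reading that the planned interaction is a change-score comparison.

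**2. Algebra for a normal outcome without a limit.** Let σ be the per-visit SD, r the Day 1–Day 8 correlation and n = 10 per arm.
- Interaction: variance = (2/n) × 2σ²(1 − r).
- Day 8 adjusted for Day 1: variance ≈ (2/n) × σ²(1 − r²) × (1 + 1/16). The last factor is the cost of estimating the slope at N = 20.
- Ratio, adjusted to interaction: (1 + r)/2 × 17/16.

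| r | Variance ratio | Detectable difference at 80% power, in Day 8 SDs: interaction → adjusted |
|---|---|---|
| 0.3 | 0.65 × 1.0625 = 0.69 | 1.57 → 1.31 |
| 0.5 | 0.75 × 1.0625 = 0.80 | 1.32 → 1.19 |
| 0.7 | 0.85 × 1.0625 = 0.90 | 1.03 → 0.98 |
| 0.9 | 0.95 × 1.0625 = 1.01 | 0.59 → 0.60 |

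The ratio equals 1 when (1 + r)/2 = 16/17, that is, r ≈ 0.88.

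**3. Simulation with the 50-minute limit.** The documents give no median, spread or correlation for latency, so these are assumptions: log-normal latency, log-SD 1, correlation 0.5 on the log scale, active-to-control time ratio 2, and values recorded as 50 at the limit. The planned analysis is a t test on change (18 df). The alternative is least squares of Day 8 on group, Day 1 and FTND stratum (16 df). There were 10,000 trials per setting, with Monte Carlo SE at most 0.5 percentage points.

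| Control median (min) | Power, planned → adjusted | SE (min), planned → adjusted | Variance ratio, planned/adjusted | Equivalent N under the planned test (20 × ratio) |
|---|---|---|---|---|
| 10 | 29% → 32% | 6.6 → 6.1 | 1.15 | 23 |
| 20 | 26% → 33% | 7.7 → 6.8 | 1.31 | 26 |
| 30 | 23% → 30% | 7.6 → 6.4 | 1.43 | 29 |
| 40 | 19% → 26% | 7.2 → 5.9 | 1.50 | 30 |

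Type I error is 4.6–5.0% planned and 4.6–5.1% adjusted. The mean estimates of the two analyses agree within about 0.3 minutes.

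**4. Other assumptions** (power in %, medians 10/20/30/40, ratio 2 unless stated).

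| Setting | Planned | Adjusted |
|---|---|---|
| r = 0.3 | 23/21/19/16 | 29/28/27/24 |
| r = 0.7 | 40/36/31/25 | 41/41/37/33 |
| r = 0.9 | 75/69/57/46 | 73/70/62/55 |
| Log-SD 0.7 | 56/51/40/30 | 58/60/55/46 |
| Ratio 3 | 62/50/41/32 | 66/64/58/49 |
| All three Section E1 factors as covariates, unrelated to latency | 29/26/22/19 | 31/31/29/26 |

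**5. Bayesian analysis.** The default prior for a regression coefficient is normal with mean 0 and variance 100, so its SD is 10. On the minutes scale this is comparable to the standard errors above, so it is not flat. In the planned model it also shrinks chance Day 1 imbalance between arms, which recovers much of what adjustment would give. With this prior and variances plugged in (not full MCMC), the chance of reaching the plan's 0.75 posterior threshold at ratio 2 is about 81/78/75/71% planned and 79/78/76/74% adjusted. Under no effect it is about 20–21% planned and 21–23% adjusted.

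**The case against.** The case for leaving the plan as it is has real strength. Both analyses estimate the same difference with type I error near 5%, so choosing the interaction is not an error. At ratio 2 and correlation 0.5 the gain is 3 to 7 percentage points, and power is at most 33% either way. At correlation 0.9 and median 10 the planned test is marginally better (75% against 73%). The plan describes itself as exploratory and hypothesis-generating and presents frequentist power only as due diligence. The algebra is also not special to latency: craving, heart rate and cortisol share the same model. All of this stands, and it limits the point to precision. It does not remove the point, because the gain costs nothing in data collection.

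A reader might go further and infer any of four things, none of which the documents support.
- **That the limit makes the planned test invalid.** Recording 50 gives a valid comparison of mean latency within 50 minutes. Its size is bounded, but Hypothesis 1 claims only longer latency and promises no effect on unrestricted latency.
- **That the value at the limit is open.** The analysis text states no rule. But the payment text refers to a maximum latency, and the stated $34 equals 2 × ($10 + $7), so 50 is the natural value.
- **That participants at the limit would be dropped as missing.** Nothing in the plan suggests this. Even for missing data it says "Analyses will address non-ignorable missingness using pattern-mixture modeling".
- **That adjustment also helps the Bayesian analysis.** Under the default prior it largely does not.

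**Conclusion.** The point holds as a matter of frequentist precision for one primary outcome. Under the stated assumptions, adjusting Day 8 latency for Day 1 gives the precision that the planned test would have with about 23 to 30 participants instead of 20. The gain is larger at low or moderate between-day correlation and when controls wait longer. It is little or none at a correlation of about 0.9 with controls who smoke early. Every size quoted depends on an assumed latency distribution, because the documents supply none.

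No Bayesian gain should be claimed: at medians 10 to 30 the two models reach the threshold about equally often, and at 40 adjustment is only slightly ahead. The absence of a written recording rule at 50 minutes is a minor gap in wording. Neither matter invalidates the trial. The change is worth making before analysis.

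**What to change.** 1. For the frequentist analysis of latency, replace the time-by-group interaction test with a model of Day 8 latency on treatment group, Day 1 latency and the stratification factors actually used. Study Design and Section E1 list different factors, so name them. State the target as the difference in mean latency within 50 minutes.
2. Use the same mean model in the Bayesian analysis for consistency, without claiming that it is more sensitive.
3. As a clarification, state that a participant who has not smoked by 50 minutes is recorded as 50, whatever is bought afterwards, and report the proportion reaching 50 minutes in each arm.
4. A right-censored log-normal or Weibull model may be added as an optional supportive analysis. It adds no power beyond Day 1 adjustment. It is also imprecise at N = 20: for a true ratio of 2, the 10th to 90th percentile of estimates is 1.1–4.0 at control median 30.

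**Cost.** SAP wording and model code; no new data. Residual degrees of freedom fall from 18 to 16 with FTND alone, or to 14 with three factors. There is no gain, and possibly a very small loss, if the two days correlate at about 0.9 and controls smoke early.

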### **Measures**

**Baseline Screening** As part of the CNRA general evaluation protocol (HSC-MS-05-0322), to determine eligibility, participants will receive a comprehensive medical and psychiatric evaluation including: a medical-history questionnaire, physical examination, laboratory chemistries (e.g., blood chemistry screen, complete blood count, urinalysis and urine pregnancy test), and ECG. Clinicians will conduct the **SCID**, the **ASI**, the **KMSK** assessment of lifetime substance use interview, and **TLFB**.

**Smoking-Related Measures** Nicotine dependence will be assessed using the **FTND**. Self-report will be used to collect self-reported number of cigarettes used in the past 7 days. Nicotine craving will be assessed using a brief, 10-item version of the **Questionnaire of Smoking Urges (QSU-brief)**. Nicotine withdrawal will be assessed using the 8-item **MNWQ**. **Breath CO** will be used to measure severity of smoking and overnight smoking abstinence.

**Sleep-Related Measures** Quality of sleep in the past week will be primarily assessed using the **PROMIS Sleep Disturbance Short Form**, a well validated and reliable subjective measure of sleep quality. Secondary measures will include the **Epworth Sleepiness Scale**, and **PSQI**. Sleep actigraphy (total hours, levels, and movement) will be measured via the Garmin Vivosmart® 3 device as validated by recent research.

**Stress and Anxiety Measures** Stress and anxiety will be assessed using standard, validated questionnaires using the **HAM-A**, **PSS**, and **DASS-21**. Additionally, a single-item **VAS** measure will be used to assess self-reported stress.

**Human Laboratory Measures** Experimental measures will be conducted on study days 1 and 8. Participants will be instructed to stop smoking by 10 pm the day before, in order to ensure they meet the breath CO criterion ( $CO \leq 4$  ppm) indicating overnight abstinence. In addition to measuring nicotine craving and withdrawal using the QSU and MNWQ, respectively, we will conduct two additional assessments.

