## DATA ANALYSIS PLAN

**Confounding Variables** Preliminary data analyses will inspect relationships between baseline/demographic variables, experimental group, and specified outcome variables via traditional statistical tests (e.g., chi-square, Mann-Whitney-Wilcoxon, Kruskal-Wallis, and *t*-tests). Baseline covariates that demonstrate a relationship with both assigned group and outcome variables meet criteria for being potential confounders and will be included as a covariate in any statistical models for hypothesis testing. All analyses will statistically control for the stratification variables (detailed above in the Study Design section).

**Inferential Paradigm** Following recommendations for clinical trials in the literature analyses will proceed using parallel frequentist and Bayesian statistical inference. Frequentist results yield The probability of the data (or data more extreme), given the null hypothesis, while Bayesian results yield The probability of the null hypothesis given the data and The probability of the alternative hypothesis given the data.

alternative hypothesis. If possible, Bayesian analyses will incorporate informative priors as they develop in the literature; otherwise, weakly informative priors will be incorporated as a default (e.g., for regression coefficients:  $\sim N[\mu=0, \sigma^2=100]$ ; for non-linear outcomes this prior applies to the coefficient within the link-function). Sensitivity analyses using optimistic and pessimistic, skeptical priors will evaluate prior assumptions. Assessing the convergence of Bayesian analyses on the posterior distributions via Monte-Carlo Markov chain (MCMC) will use graphical (Trace Plot, Autocorrelation Plot) and quantitative (Geweke Diagnostics, Gelman-Rubin Diagnostics, and Heidelberger-Welsh Diagnostics) evidence. Evaluation of posterior distributions will permit statements regarding the probability that effects of varying magnitudes exist, given the data. Statistical analyses will use SAS v. 9.4 and the most up-to-date stable release version of the R statistical computing environment using packages rstan and brms.

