## DATA SAFETY MONITORING PLAN

### **E1. Human Subjects Involvement and Participant Characteristics**

The study will test 20 current cigarette smokers, 18 to 65 years old that report smoking at least 10 cigarettes/day (half pack). Notably, because the study medication (suvorexant) is contraindicated with alcohol use, we will exclude subjects with alcohol use disorders (via screening at intake). We will also exclude those individuals meet DSM-5 criteria for an alcohol use disorder or report recent problem drinking (5/4 drinks for males/females in < 2.5 hours or > 10 alcoholic drinks per week) or those who report being unwilling to stop using alcohol in the evening for the two weeks of the study. Additional exclusion criteria include individuals that are pregnant, nursing, or planning on becoming pregnant during the course of the study; or if they have any other illness, condition, or use of medications which in the opinion of the PI and/or admitting physician would preclude safe and/or successful completion of the study. This will be accomplished via full medical evaluation at intake by [name], M.D., CNRA Medical Director. The study will be conducted at the Neurobehavioral Research Laboratory at the CNRA. Recruitment strategies will include local advertising in print media, public service announcements on radio, and referrals to CNRA in the Houston metropolitan area. We expect to enroll a minimum of 2 participants per month to meet recruitment goals; however, we will be able to accommodate four simultaneous participants. Participants will be required to participate for 3 days (intake/screening, baseline observations, and one follow-up observation one week later). Research data will be collected at each scheduled time point.

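### For outcomes with one roughly normal value per visit, the planned time-by-group test is a change-score comparison that leaves the Day 1 value unused as a covariate and so gives up some precision

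*Combined protocol and SAP*

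**What the plan says.** The Hypothesis 1 model under Specific Analyses takes each outcome "as a function of the main effects and interaction between time (pre vs. post) and treatment group". The remaining terms of that model are then given in these words: "including any necessary control variables (as defined above in the confounding variables section) and a random intercept for participant". Hypothesis 2 uses the same form for the sleep metrics. Under Statistical Modeling, continuous outcomes get the normal family and identity link.

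The Confounding Variables paragraph adds two kinds of adjustment. First, "All analyses will statistically control for the stratification variables". Second, a baseline variable related to both assigned group and outcome "will be included as a covariate in any statistical models for hypothesis testing". No covariate-by-time term is stated, and the Day 1 outcome is nowhere named as a covariate.

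On timing, the Measures section states "Experimental measures will be conducted on study days 1 and 8", and for the cold pressor "Stress reactivity will be assessed using a modified version of the CPT on study days 1 and 8". Section E1 describes the last two visits as "baseline observations, and one follow-up observation one week later". Under Study Medication & Medication Compliance, "participants will be informed to take the medication at 10:00 PM". Day 1 testing therefore appears to precede the first dose. That is an inference; no sentence says so directly.

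**The concern.** In this model the pre-treatment measurement is one of the two response rows. With two visits and a random intercept, the interaction subtracts each person's Day 1 value from the Day 8 value in full, whatever the correlation between them. When that correlation is low or moderate, full subtraction adds noise.

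The promised control for strata and confounders looks as though it would help. As main effects, however, these terms act on a person's level, and level has already cancelled within person. The plan therefore states an adjustment that does not reach the contrast it tests. With N capped at 20 and 80% power reported only for a large effect, precision available from data already collected is worth having.

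**Working it through.** **Inputs.** From the documents: N = 20, 10 per arm; alpha 0.05 (taken as two-sided); f = 0.66 for 80% power; the model above. Assumed, because the documents do not give them: the Day 1/Day 8 correlation rho, equal variances at the two visits, and that f is on the SD of change.

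**1. The plan's own figure.** Two groups, F test on (1, 18) df, noncentrality = f² × N = 0.66² × 20 = 8.712. Power is 0.797, and f for exactly 80% is 0.662. The stated figure reproduces. It corresponds to a two-sample test on one value per person, so it fits a comparison of change scores with d = 2 × 0.66 = 1.32 SD of change.

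**2. What the interaction estimates.** On one simulated complete dataset of 20:

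| Model | Treatment estimate | SE |
|---|---|---|
| Planned, no stratum | 0.8300 | 0.5207 |
| Planned, stratum as main effect | 0.8300 | 0.5207 |
| Planned, stratum-by-time added | 0.9483 | 0.5277 |
| Day 8 on group and Day 1 value | 0.6150 | 0.4477 |
| Common Day 1 mean, unstructured covariance (ML) | 0.6150 | – |

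The difference in mean change is 0.7364 − (−0.0936) = 0.8300. In 60 further datasets at each of rho 0.3, 0.5 and 0.7, the planned interaction equalled the difference in mean change to about 1e-15, with or without two strata as main effects. Four fits at rho 0.3 were set aside for a random-intercept variance near zero or a failed fit. The t statistic matched the change-score test to within 6e-5, except at rho 0.3 with strata, where it differed by up to 0.15 while the estimate was still identical. Entering the Day 1 outcome itself as a main effect also left the estimate unchanged.

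**3. Size of the loss.** Per-person variance, in units of the single-visit variance:
- change score: 2(1 − rho)
- Day 8 adjusted for Day 1: 1 − rho²
- ratio, adjusted to change: (1 + rho)/2

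Estimating the Day 1 slope inflates the variance of the adjusted contrast by 1 + 1/16 = 1.0625 on average. The adjusted noncentrality is therefore 8.712 × 2/(1 + rho)/1.0625, on (1, 17) df.

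| rho | Variance ratio | Noncentrality | Power, formula | Power, simulated |
|---|---|---|---|---|
| 0.3 | 0.65 | 12.61 | 91.7% | 92% |
| 0.5 | 0.75 | 10.93 | 87.6% | 88% |
| 0.7 | 0.85 | 9.65 | 83.3% | 84% |
| 0.8 | 0.90 | 9.11 | 81.2% | 81% |
| 0.9 | 0.95 | 8.63 | 79.1% | 79% |

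The simulated column rests on 16,000 trials per setting. The planned test stays at 79–80% throughout, and the two are equal at rho = 0.87. In single-visit SDs, the difference detectable with 80% power (change score vs adjusted) is 1.57 vs 1.31 at rho 0.3, 1.32 vs 1.19 at 0.5, 1.03 vs 0.98 at 0.7, and 0.59 vs 0.60 at 0.9.

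**4. Chance imbalance is the same loss.** The variance difference per person is 2(1 − rho) − (1 − rho²) = (1 − rho)². Multiplied by 2/n, this is exactly the variance of (1 − rho) times the Day 1 arm difference. The planned SE already contains it.

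**5. Type I error.** Simulated size was 4.6–5.6% for the change-score and Day 1-adjusted tests. A common-Day-1-mean model with a random intercept and a z test gave 7.0, 7.0, 6.6 and 6.4% at rho 0.3, 0.5, 0.7 and 0.9. With a t reference on 17 df it gave 5.3, 5.5, 5.2 and 4.9%.

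**6. Adding randomisation factors by time.** With non-prognostic binary factors, power at rho 0.3/0.5/0.7 was 91/87/83% (one factor, permuted blocks) and 90/86/82% (one factor, urn). With three factors by urn it was 86–87/81–82/76–77%, and with three independently drawn factors 84/79/74%. Break-even rho is about 0.81–0.86 with one factor and about 0.5–0.6 with three.

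**The case against.** The strongest reply is that both estimators are valid and little turns on the choice in a pilot that the plan itself describes as exploratory. The stated target is change over time by group, which the interaction estimates without bias under randomisation. On the plan's posterior threshold of 0.75 (flat prior and directional reading assumed), the chance of a signal at f = 0.66 is 98.8% as planned and 99.8, 99.6 and 99.2% adjusted at rho 0.3, 0.5 and 0.7. At d = 0.5 it is 67% against 74, 71 and 69%. This stands, and it limits the weight of the point.

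The scope objection also stands. Latency is capped at 50 minutes and falls outside. Heart rate and cortisol qualify only if each visit is reduced to one value, which the plan does not say. Sleep duration and restlessness appear to come from actigraphy, and the documents do not clearly show a pre-dose value. With missing visits or a non-identity link the cancellation is only approximate, and informative priors can move the Bayesian result.

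A reader might infer that chance Day 1 differences are a further harm: with 10 per arm the SD of the arm difference is √(2/10) = 0.447 SD, so a gap of at least 0.5 SD has probability 26%. Step 4 shows that this is the precision loss restated. For the QSU the 26% may also be too high, because section E1 stratifies on QSU-brief. With a 50/50 split and perfect balance assumed, it becomes about 6, 15 or 22% when the stratifying and Day 1 scores correlate at 1, 0.8 or 0.5.

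The confounder rule is not a rescue: even if it admitted the Day 1 outcome, a main effect would not change the treatment estimate.

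**Conclusion.** The point holds within its scope: one approximately normal value per visit, a confirmed pre-treatment value, and complete pairs. The QSU meets this clearly and PROMIS sleep quality probably; heart rate and cortisol do if reduced to one value per visit. For these outcomes the planned test is a change-score comparison, and control variables entered as main effects do not alter its estimate.

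The algebra is certain. The size depends on rho, which the documents do not give: a gain of roughly 12 percentage points of power at rho 0.3, about 4 at 0.7, and a slight loss above about 0.87.

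A reader might go further and conclude that the planned test is biased or invalid, or that f = 0.66 is wrong. Neither follows: the test is valid under randomisation, and the figure reproduces. Nor do the calculations support requiring every randomisation factor to interact with time. If non-prognostic, three such terms take power below the planned test above rho of about 0.5–0.6. This is a worthwhile, inexpensive improvement to an exploratory pilot.

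**What to change.** For each outcome in scope, state that the treatment effect is adjusted for the Day 1 value, by one of two routes:
- regress Day 8 on group and the Day 1 value; or
- keep the mixed model but constrain the arms to a common Day 1 mean (time and time-by-group, no group main effect), with an unstructured 2×2 covariance and small-sample degrees of freedom such as Kenward-Roger, not a z test.

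The second route still gives within-arm change and keeps people with one missing visit. With complete pairs its treatment estimate matches the first. Its size with Kenward-Roger degrees of freedom was not simulated here; that of the equivalent regression was. Use the same mean structure in the Bayesian fit. State that Day 1 measures are taken before the first dose, and list the outcomes to which the rule applies.

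A factor-by-time term is optional. If one is wanted so that control for stratification reaches the treatment contrast, limit it to a single pre-stated factor. First reconcile Study Design (FTND only) with section E1 (sex, FTND and QSU-brief).

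The cost is wording only, with no new data. Residual df fall from 18 to 17 with the Day 1 value, and to 16 with one factor. Power is slightly lower than planned if rho exceeds about 0.87, or about 0.81–0.86 with one non-prognostic factor.
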